6.4 Efficacy Variables

6.4.1 Primary Efficacy Variable(s)

6.4.1.1 Quantitative assessment of images for Flortaucipir (SUVr based)

For the Flortaucipir image, standard uptake value ratios (SUVr) will be calculated to estimate tau load globally and for each individual region. For global assessment, a target region derived statistically with a Multiblock Barycentric Discriminant Analysis (MUBADA) method will be used; at individual region level, VOIs determined in the AAL atlas masked to exclude white matter and CSF for parietal, temporal, occipital, anterior hippocampal parahippocampal and fusiform gyri will be applied. For all SUVr value calculations, a selected white matter region derived using a parametric estimated signal reference intensity (PERSI) method will be used as reference region.

6.4.1.2 Qualitative assessment for Flortaucipir and Diagnostic Performance

At the exploratory phase, the baseline flortaucipir scan images will be visually interpreted by Avid's imaging experts. The scans will be classified as either

- AD pattern (AD+)
- AD pattern and likely to progress (AD++)
- Not consistent with an AD pattern (AD-)

AD++ also is referenced as Tau+ in the SAP, and the rest is referenced as Tau-.

6.4.2 Secondary Efficacy Variables

6.4.2.1 Amyloid Beta Status Based on Florbetapir

Florbetapir F 18 images will be assessed by expert readers blinded to the diagnostic group for the subjects. The images will then be classified as either AB+ (amyloid positive) or AB- (amyloid negative). For images read by more than one reader, the majority or consensus read will be used for each subject.

6.4.2.2 Quantitative Imaging for Florbetapir (SUVr based)

For the Florebetapir 18 F image, the global cortical average SUVr will be calculated as the average across these six target brain regions: the medial frontal cortex, temporal cortex, parietal cortex, posterior cingulate cortex, anterior cingulate cortex and the precuneus with entire cerebellum as a reference region.

6.4.2.3 Cognitive and Functional Assessments

Except for Clinical Dementia Rating (CDR) scale, cognitive assessments will be performed at screening or baseline, at follow-up visits (9 (+/- 2) months, and 18 (+/- 2) months) during the study. CDR scales will be performed at 9 months and 18 months visits only. These cognitive assessments include the following:

Mini-Mental State Examination (MMSE)

The MMSE (Folstein et al., 1975) is a brief instrument used to assess cognitive function in elderly patients. The instrument is divided into 2 sections. The first section measures orientation, memory, and attention. The maximum score for the first section is 21. The second section tests the ability of the patient to name objects, follow verbal and written commands, write a sentence, and copy figures. The maximum score for the second section is 9. The range for the total MMSE score is 0 to 30, the sum of each correct answer, with higher scores indicating better cognition.

Alzheimer's Disease Assessment Scale—Cognitive subscale (ADAS-Cog11)

The ADAS (ADAS-Cog; Rosen et al. 1984) was designed to assess the severity of the dysfunction in the cognitive and noncognitive behaviors characteristic of persons with AD. The cognitive subscale of the ADAS, the ADAS-Cog11, consists of 11 items assessing areas of function most typically impaired in AD: orientation, verbal memory, language, and praxis. The overall score for ADAS-Cog11 ranges from 0 to 70, with higher scores indicating greater disease severity, and is calculated as the sum of all 11 individual component scores.

Digit Symbol Substitution Test (DSST)

The DSST (Wechsler Adult Intelligence Scale F Revised, 1981) is a paper test of psychomotor performance in which the subject is given a key of numbers and matching symbols and a test section with numbers and empty boxes. Under each number the subject should write down the corresponding symbol as fast as possible. The score is the number of correct number-symbol matches made within the allowed time (90 seconds). The strategy to solve the DSST consists of sequential encoding and retrieval of numbers and corresponding symbols. Incidental memory, visuo-motor coordination, perceptual organization, and selective attention are key factors that determine the final score (Wechsler Adult Intelligence Scale Revised, 1981). The ability to sort out irrelevant information (e.g., symbols that may look alike) also impacts performance. This test has high test-retest reliability (Matarazzo and Herman, 1984). One point is given for each symbol correctly drawn during the ninety seconds, with the maximum score of 93. Greater totals denote lower disease severity.

Digit span forward and backward (from Wechsler Memory Scale-Revised (WMS-R))

Digit Span is composed of two tasks administered independently of each other: Digits Forward and Digits Backward. On both tasks, the examiner reads a series of number sequences to the subject. For each Digits Forward item, the subject is required to repeat the number sequence in the same order as presented. For Digits Backward, the subject is required to repeat the number sequence in the reverse order. The score ranges from 0-24, a maximum score of 12 for digit span forward and a maximum score of 12 for digit span backward, with lower scores indicating greater disease severity.

Trail Making A and B

The trail making test (Reitan and Wolfson, 1985) is a test of executive function. Part A consists of 25 circles numbered 1 through 25 distributed over a sheet of paper. The subject is instructed to connect the circles by drawing a line as quickly as possible in ascending numerical order. Part B consists of 25 circles containing either numbers (1 through 13) or letters (A-L). The subject is instructed to connect the circles while alternating between numbers and letters in ascending order. The subject is timed. The total score is the time to complete Part A, with a maximum of a 150 seconds and Part B with a maximum of is a 300 seconds. Timing is not stopped while correcting errors. Testing is stopped if the maximum time is reached. The total score is the number of seconds to complete both trails, where higher scores indicate greater disease severity.

Logical Memory Test, Immediate and Delayed Recall, Story A (WMS-R)

The logical memory test (Wechsler D. 1987) assesses the ability to recall a short story. Subjects are read a story and asked to recall the story immediately and after a delay. The

maximum score is 25, and each point obtained based on how much of the story is correct. Higher scores indicate better cognition.

Animal List Generation

The animal list generation (Morris et al. 1989) is used to measure verbal fluency. The subject is asked to name as many animals as possible in 60 seconds. The total score is the count of all admissible words, where lower scores denote greater cognitive impairment.

Boston Naming Test (BNT) (30 item)

The 30 item Boston Naming Test (Kaplan, et al. 1983) is a measure of the ability to orally label 30 line drawings of objects. The objects are presented to the subject in order of frequency, from most frequent to least frequent. The maximum score is 30, where higher scores indicate better cognition, obtained from the number of spontaneously given correct responses in addition to the number of correct responses following a stimulus cue.

American National Adult Reading Test (ANART)

ANART (Grober and Sliwinski 1991) is a measure for estimating premorbid verbal intelligence. The subject is presented with a word list and asked to pronounce the words. One point is given for each correctly pronounced word, with a maximum score of 45, where lower scores indicate greater disease severity.

Clock Drawing Test

The clock drawing test (Goodglass and Kaplan 1983) has two components: a command condition and a copy condition. In the command condition, the subject draws a clock according to verbal instructions. In the copy condition, the subjects copy a model clock drawn at the top of a form. The score ranges from 0-5 where a point is obtained from approximately circular face, symmetry of number placement, correctness of numbers, presence of two hands, and presence of two hands set to the correct time. Higher scores suggest better cognition.

Benton Judgment of Line Orientation Test (JOLO)

The JOLO (Benton 1978) is a non-motor measure of visual perceptual ability where there is no time demand. The task asks subjects to match two lines by their angle of orientation to a test set of lines presented below the stimulus lines. Each correct response is given one point and the maximum score is 30, where higher scores denote lesser disease severity.

Pfeffer Functional Activities Questionnaire (FAQ), (Pfeffer et al. 1982)

Functional status is conceptualized as the “ability to perform self-care, self- maintenance and physical activities.” The FAQ was developed to assess instrumental activities of daily living involving higher level functional skills such as shopping alone, writing checks, remembering appointments, etc. The FAQ asks informant to rate patient’s ability using the following scoring system: Dependent = 3; Requires assistance = 2; Has difficulty but does by self = 1; Normal = 0; Never did [the activity] but could do now = 0; Never did and would have difficulty now = 1. The sum scores ranges from 0-30, where higher scores indicate greater cognitive impairment.

6.4.2.3.1 Clinical Meaningful Changes

Clinically meaningful changes will be defined by categorizing the change in psychometric scores, as follows:

1. a 3 point or more drop in MMSE relative to baseline;
2. a 4 point or more increase in ADAS Cog 11 relative to baseline;
3. a 3 point or more increase in FAQ relative to baseline ;
4. a 1 point or more increase in CDR SB relative to 9 month ;
5. a 12 point or more increase in ADAS+FAQ composite relative to baseline
6. CDR global score will be categorized as decreasing; stay the same; increasing from 9 month.

6.4.3 Additional Efficacy Variables

6.4.3.1 ApoE Genotyping

ApoE genotyping will be performed at the initial Flortaucipir imaging session for those subjects whose ApoE is unknown. For analysis purposes, subjects will be categorized as ApoE ϵ 4 positive (ϵ 4+) if at least one allele is an ϵ 4 allele and ApoE ϵ 4 negative (ϵ 4-) if neither allele is an ϵ 4 allele.

6.4.3.2 Genetic Samples

A one-time blood collection (10 mL, blood) will be performed on the day of the initial Flortaucipir imaging session for genetic analysis. Where local regulations allow, samples will be stored and analysis may be performed on genetic variants thought to play a role in dementia or related diseases. Samples will only be used for investigations related to disease and drug or class of drugs under study in the context of this clinical program. They will not be used for broad exploratory unspecified disease or population genetic analysis. No prospective analyses will be performed using this data.

6.4.3.3 MRI Scan of the Brain

MRI, including both volumetric and standard clinical sequences, will be conducted at each tau scan visit. Volumetric measurements, including the whole brain, grey matter, ventricle, and hippocampus will be performed. The brain volumes will be normalized for analysis purpose.

6.4.3.4 Optional Cerebrospinal fluid (CSF) collection by Lumbar Puncture (LP)

Some subjects (depending on site participation) who are ≥ 50 years of age who qualify for the study will be offered to consent for optional CSF collection by LP. The LP should be performed at least 48 hours apart from the PET imaging sessions and should be performed within +/- 60 days of the initial Flortaucipir Imaging Visit. Each LP will be done by a qualified physician who is experienced in performing the procedure. Subjects, or their designated decision maker, will call the investigator to report any adverse events associated with the LP procedure. The CSF will be assessed for biomarkers of neurodegeneration and neurological disease (tau, phosphor-tau and beta-amyloid (AB)).

6.5 Drug Concentration Measurements and Pharmacokinetic Parameters

6.5.1 Handling of Pharmacokinetic Parameter Outliers

No pharmacokinetic parameters or drug concentration measurements will be collected during this study.

6.6 Safety Assessments

6.6.1 Extent of Exposure and Compliance to Study Treatment

During the florbetapir F 18 imaging session, subjects will receive a single IV bolus administration target dose of 370 MBq (10 mCi) of florbetapir F 18 injection followed by a 10 minute PET brain scan (2 acquisitions of 5 minute duration) at 50 minutes post injection. During the Flortaucipir imaging session, all subjects will receive a single IV bolus administration target dose of 370 MBq (10 mCi) of Flortaucipir injection. At approximately 80 minutes post dose, scanning will begin. Four 5-minute acquisitions will be taken. Exposure to study drug will be summarized using the total administered dose at each scan visit for Flortaucipir and Florbetapir F 18 injection respectively.

6.6.2 Adverse Events

The investigator's verbatim term of both serious and non-AEs will be mapped to system organ class (SOC) and preferred terms using the current version of the Medical Dictionary for Regulatory Activities (MedDRA).

Treatment-emergent AEs (TEAEs) are undesirable experiences, signs, or symptoms that begin or worsen in intensity or frequency at the time of or after the administration of study drug, and prior to the end of observation windows defined as following: the TEAE window for Flortaucipir will be from injection of Flortaucipir until 48 hours post Flortaucipir injection. For florbetapir F 18, the TEAE window will be from injection of florbetapir F 18 until 48 hours post florbetapir injection. The injection of florbetapir and flortaucipir dosages will be at least 48 hours apart. Trial-emergent AEs are undesirable experiences, signs or symptoms happened after subjects' enrollment to this trial but before the exploratory phase imaging sessions, or between the florbetapir and flortaucipir sessions but outside the 48 hour windows following the administering of Flortaucipir or Florbetapir F 18 injection. These will be recorded on the AE page of the electronic case report form (eCRF). Any event happens during study visits will be captured in medical history form, unless the site physicians consider they are related to the study drugs.

Serious AEs (SAEs) are events that result in one of the following outcomes or constitute one of the following events:

- Death
- Initial or prolonged hospitalization (other than that required by protocol; "social hospitalization" or any hospitalization for non-medical reasons does not constitute an SAE)
- A life-threatening experience (that is, immediate risk of dying)
- Persistent or significant disability/incapacity
- Congenital anomaly/birth defect
- Considered significant by the investigator for any other reason

Important medical events that may not result in death, are life-threatening, or require hospitalization may be considered serious adverse drug events when, based upon appropriate medical judgment, they may jeopardize the patient and may require medical or surgical intervention to prevent one of the outcomes listed in this definition.

For the summarization of TEAEs by seriousness, events recorded with missing seriousness will be summarized as serious.

Investigators will be instructed to report their assessment of the potential relatedness of each AE to protocol procedure, concomitant medication, and/or investigational product. The assessment of the relationship of an AE to the administration of the investigational product is a clinical decision based on all available information at the time of the completion of the eCRF. For the summarization of TEAEs by relationship to study drug or protocol procedure, events recorded with missing relationship will be summarized as Related.

In addition to assessing the relationship of the administration of the investigational product to AEs, an assessment is required of the severity of the event. The following classifications should be used:

Mild:

A mild AE is an AE, usually transient in nature and generally not interfering with normal activities.

Moderate:

A moderate AE is an AE that is sufficiently discomforting to interfere with normal activities.

Severe:

A severe AE is an AE that incapacitates the subject and prevents normal activities. Note that a severe event is not necessarily a serious event. Nor must a serious event necessarily be severe.

For the summarization of TEAEs by intensity, events recorded with missing intensity will be summarized as Severe.

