Potential genotoxicity of non-radioactive AV-1451 was tested in both *in vitro* and *in vivo* assays. In the *in vitro* assays, AV-1451 tested positive for potential genotoxicity. However, in the *in vivo* rat micronucleus assay at doses up to 750x MHD (scaled allometrically), AV-1451 showed no evidence of genotoxicity. The different results in the *in vitro* genotoxicity assays and the *in vivo* micronucleus study are likely related to differences in the exposure conditions encountered by the target cells in the different test systems. *In vivo*, AV-1451 is cleared rapidly; however, the *in vitro* experiments employ static, prolonged exposure of cells to high concentrations of the test article. While the *in vitro* data show the potential for genotoxicity, the *in vivo* data provide assurance that genotoxicity is unlikely to occur at clinically-relevant doses for human diagnostic studies.

¹⁸F-AV-1451 has been evaluated in two human studies under the exploratory IND (Chien, et. al). Adverse events reported have been mild and transient; none have been considered related to ¹⁸F-AV-1451 administration. Preliminary evaluation of the PET images suggest that ¹⁸F-AV-1451 is eliminated from normal brain yielding only a diffuse pattern of background activity ([Figure 1](#)), whereas a regionally-specific gray matter distribution is observed in subjects with high probability AD ([Figure 2](#)).

[figure not shown]

Figure 1: [REDACTED] control subject (MMSE = 29)

[figure not shown]

Figure 2: [REDACTED] AD subject (MMSE = 18)

Human dosimetry has been obtained in nine subjects. Generally, the radiotracer distribution was consistent among the subjects and showed rapid hepatobiliary clearance. There were three organs that received estimated doses higher than 0.05 mSv/MBq. The organ that received the largest estimated dose was the upper large intestinal wall (0.0962 ± 0.0134 mSv/MBq), followed by the small intestine and the liver. The Effective Dose was 0.0241 ± 0.0016 mSv/MBq. This results in an estimated Effective Dose of 8.92 mSv for an anticipated 370 MBq (10 mCi) injection and is comparable to the effective dose of approved ¹⁸F-labeled compounds such as fluorodeoxyglucose (FDG) and florbetapir F 18 injection.

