7.7.2. Adverse Event Definitions

Adverse Events

For reporting purposes, Avid will distinguish among pre-existing conditions, treatment - emergent adverse events and trial-emergent adverse events. Pre-existing conditions (i.e., undesirable experiences, signs or symptoms that begin prior to the Screening Visit) will be recorded on the medical history and/or physical exam eCRF pages. Signs and symptoms that are believed to be due to the pre-existing condition (started prior to dose of study medication) do not have to be recorded in the AEs section of the eCRF, unless there is an increase in frequency or severity. Additionally, signs or symptoms or changes in pre-existing conditions that occur outside the trial defined adverse event reporting period (e.g., between the end of the baseline/cross-sectional imaging period and the 9 month follow-up imaging period) will be recorded in medical history.

An adverse event is any untoward medical occurrence associated with the use of a drug in humans, whether or not considered drug related. For the purposes of this study, untoward medical occurrences will be considered associated with the use of ¹⁸F-AV-1451, and thus be reported as adverse events, if they occur within 48 hours after ¹⁸F-AV-1451 administration, either at baseline or at the 9 or 18 month imaging visit. Untoward medical occurrences will be considered associated with the use of Florbetapir F 18 injection, if they occur within 48 hours after Florbetapir F 18 injection administration. Adverse events associated with the use of ¹⁸F-AV-1451 or Florbetapir F 18 injection will be recorded as treatment emergent relative to the respective drug. Adverse experiences that occur after administration of either drug but outside the 48 hour reporting window will not be reported unless the investigator believes they are attributable to the drug.

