In order to capture possible adverse effects of trial participation, trial-emergent adverse events will also be reported as any untoward medical occurrences occurring, during the baseline/cross-sectional imaging period but not during the 48 hour windows following the administration of ¹⁸F-AV-1451 or Florbetapir F 18 injection. For this purpose, the baseline/cross-sectional imaging period will be defined as beginning with the signing of consent and ending 48 hours after the last of the screening/baseline procedures described in sections [7.1.1 – 7.1.3](#), including (but not limited to) neuropsychological testing, MRI, ¹⁸F-AV-1451 or Florbetapir F 18 injection PET scanning and lumbar puncture.

The end of study for the purpose of adverse event reporting is defined as 48 hours after the last administration (i.e., 18 month visit or early termination visit) of ¹⁸F-AV-1451.

Serious Adverse Event (SAE)

An SAE is an AE that results in one of the following outcomes or constitutes one of the following events:

- Death;
- Initial or prolonged inpatient hospitalization (other than that required by protocol; “social hospitalization” or any hospitalization for non-medical reasons does not constitute an SAE);
- A life-threatening experience (that is, immediate risk of dying);
- Persistent or significant disability/incapacity;
- Congenital anomaly/birth defect;
- Considered significant by the investigator for any other reason.

Important medical events that may not result in death, be life-threatening, or require hospitalization may be considered serious adverse drug events when, based upon appropriate medical judgment, they may jeopardize the patient and may require medical or surgical intervention to prevent one of the outcomes listed in this definition.

Unexpected Adverse Event

An unexpected adverse event is an adverse event not previously reported or an adverse event that occurs with specificity, severity or frequency that is not consistent with the current investigator’s brochure.

Relationship to Investigational Product

Investigators will be instructed to report their assessment of the potential relatedness of each adverse event to protocol procedure, concomitant medication and/or investigational product. The assessment of the relationship of an adverse event to the administration of the investigational product is a clinical decision based on all available information at the time of the completion of the eCRF.

Intensity/Severity of an Adverse Event

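### SAP 6.6.2 sends events during study visits to medical history unless drug-related, contrary to Protocol 7.7.2 and the SAP's own 48-hour TEAE definition; its trial-emergent window is also too short

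*SAP*

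**What the plan says.** SAP 6.6.2 (Adverse Events) contains three rules in one paragraph.

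- **TEAE window.** An event is treatment-emergent if it begins or worsens within the window, and "the TEAE window for Flortaucipir will be from injection of Flortaucipir until 48 hours post Flortaucipir injection". A parallel 48-hour window applies to florbetapir. Neither has a causality condition.
- **Trial-emergent events.** These occur after enrolment but before the imaging sessions, or between the florbetapir and flortaucipir sessions and outside the two 48-hour windows.
- **Medical history.** "Any event happens during study visits will be captured in medical history form, unless the site physicians consider they are related" to the study drugs.

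SAP 8.7.2 restricts every AE summary to TEAEs and plans tables with related and not-related categories, for study drug and for protocol procedure.

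Protocol 7.7.2 starts from "An adverse event is any untoward medical occurrence associated with the use of a drug in humans, whether or not considered drug related". Untoward occurrences count as associated with flortaucipir (¹⁸F-AV-1451 in the protocol) "and thus be reported as adverse events, if they occur within 48 hours after" flortaucipir "administration, either at baseline or at the 9 or 18 month imaging visit". The investigator's attribution decides reporting only after the 48 hours have passed. Medical history takes signs, symptoms and changes in pre-existing conditions arising outside the reporting period. The protocol's example is the interval between the baseline imaging period and the 9-month imaging period. For trial-emergent events, the baseline period runs from consent, "ending 48 hours after the last of the screening/baseline procedures", and the procedures named include neuropsychological testing, MRI and lumbar puncture.

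**The concern.** Injection and continuous AE monitoring take place during study visits. A rule that sends events during visits to medical history unless they are judged drug-related therefore acts on the period in which the protocol wants events reported regardless of cause. Because SAP 8.7.2 tabulates TEAEs only, an event held as medical history disappears from the AE tables, and the not-related category loses the events it is meant to show. Expanding the safety database is a stated objective of both exploratory-phase components (SAP 3.1 and 3.2), so the AE counts matter.

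The trial-emergent definition has a separate gap. An event after both scans and outside both tracer windows, for example following a late lumbar puncture, is trial-emergent under the protocol but has no class in the SAP. The exception in the medical-history sentence does not rescue it, because that exception names the study drugs and not procedures.

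**Working it through.** The documents state no figure for events affected, so there is none to reproduce. The check is a comparison of texts, followed by a test of whether the effect can be sized.

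**1. Does causality matter inside the 48-hour window?**

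- Protocol 7.7.2: no. Attribution matters only after 48 hours.
- Protocol 7.7.4: no. Serious events up to 48 hours after dosing are collected however the investigator judges cause.
- Protocol 10.7: no. All adverse events go on the eCRF, related or not.
- SAP 6.6.2, TEAE definition: no.
- SAP 8.7.2: no. A not-related category presupposes that unrelated in-window events are kept.
- SAP 6.6.2, medical-history sentence: yes, for events during study visits.

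The last sentence is the only outlier. SAP 5.2, which records changes from the protocol's planned analyses, mentions only the split into two phases, so this is not a declared departure.

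**2. Does changing *during* to *between* remove the conflict?** Largely. The sentence would then resemble the protocol's rule for events outside the reporting period. It would not repair the trial-emergent window.

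**3. Trial-emergent window.** Protocol 7.1.2 and SAP 6.4.3.4 allow lumbar puncture up to 60 days either side of the initial flortaucipir scan. Protocol 7.1.1 and SAP 6.3 allow baseline testing up to 30 days either side. Either can fall after both scans. The protocol's period extends to 48 hours after the last such procedure, while the SAP's has already closed.

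**4. Can the loss be sized?** Under the literal reading,

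share of TEAEs removed = d × (1 − r),

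where d is the share of TEAEs arising during a visit and r the share judged drug-related. The documents give neither, and they do not define a study visit.

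The length of a visit relative to the window (48 × 60 = 2,880 minutes) shows how wide d could be:

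- Flortaucipir, injection to end of scan: (80 + 20)/2,880 = 3.5%.
- Florbetapir, injection to end of scan: (50 + 10)/2,880 = 2.1%.
- A stay of 4 to 8 hours (assumed): 240/2,880 = 8.3% to 480/2,880 = 16.7%.
- A follow-up visit taking several days, as the notes to the schedule in SAP 6.1 allow: up to 100%.

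Time share equals event share only if onsets are spread evenly over the window, and the documents do not address this. Illustrative values for the share removed, with d and r both assumed:

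| d | r = 0 | r = 25% | r = 50% | r = 75% |
|---|---|---|---|---|
| 3.5% | 3.5% | 2.6% | 1.8% | 0.9% |
| 50% | 50% | 37.5% | 25% | 12.5% |
| 100% | 100% | 75% | 50% | 25% |

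A range of 0.9% to 100% means that the documents do not determine the size.

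**The case against.** The strongest reply is that this is a one-word slip with little consequence. The TEAE definition beside it is unconditional, and the tables in SAP 8.7.2 make sense only if unrelated in-window events are retained. What sites record is governed by the protocol, which requires all adverse events to be recorded, so sites that follow it will enter these events on the AE page. Events after discharge are sought by a phone call made no earlier than 48 hours after injection. Laboratory, vital-sign and ECG summaries carry no causality filter. The trial-emergent gap changes no planned AE summary, since those are TEAE-only.

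Most of this stands, and it limits the consequence. It does not remove the contradiction. The paragraph gives a programmer two incompatible rules and no order of precedence. If the sentence describes how forms were actually completed, correct programming of the TEAE flag alone would not recover the misplaced events. Medical history is updated at the 9- and 18-month visits, so the route exists. The slip reading also leaves the trial-emergent window uncorrected.

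A reader might go further and infer that most TEAEs would be lost. Three arguments point that way, and none is supported.

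- Protocol section 1 says of the two earlier human studies: "Adverse events reported have been mild and transient; none have been considered related to" the tracer. If that recurred (r = 0), the literal rule would remove every visit-time event. But d would still be unknown, and two early studies do not fix r here.
- Assuming that 50% to 90% of visit-day events are judged unrelated only returns 50% to 90% of a subset of unknown size.
- Follow-up visits account for (210 × 2)/(20 + 210 × 3) = 420/650 = 65% of planned flortaucipir injections, given full enrolment and retention. That is a share of exposure, not of events lost, and the sentence covers baseline visits too.

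**Conclusion.** The contradiction is established from the text. The medical-history sentence in SAP 6.6.2 disagrees with Protocol 7.7.2, 7.7.4 and 10.7, with the TEAE definition in its own paragraph, and with the tables planned in SAP 8.7.2. It is probably a drafting slip for *between study visits*. Applied literally, it could take unrelated events inside the 48-hour window out of the TEAE tables. Whether it would do so, and for how many events, depends on what counts as a visit, on the two unknown shares, and on whether sites or programmers follow the SAP sentence or the protocol. A claim that most TEAEs would disappear is neither shown nor excluded.

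The shorter trial-emergent window is a second, smaller discrepancy that holds under either reading. Events after both scans but within the protocol's baseline period are left unclassified, with an effect on classification and listings only. Both points warrant correction because the change is small and the AE rule should have one meaning.

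**What to change.** 1. Replace the medical-history sentence in SAP 6.6.2. Events with onset or worsening within 48 hours of either tracer are TEAEs regardless of relatedness. Only events outside the protocol's reporting period go to medical history, subject to the protocol's own exceptions: attribution to the drug in 7.7.2 and, for serious events only, to the investigational product or a protocol procedure in 7.7.4. The SAP should not add a wider procedure exception of its own.
2. Replace the trial-emergent window with that of Protocol 7.7.2: from consent to 48 hours after the last baseline procedure, excluding the two tracer windows.
3. Before database lock, list medical-history entries with onset or worsening inside a tracer window and query or reclassify them. If only calendar dates are held (an assumption, since the documents do not say), flag the injection date and the next two dates.

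The cost is two SAP sentences and one data-review listing. The listing would also show whether any recorded event was misplaced, which the documents cannot.
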